6.2 Treatment Regimens

Treatment group “as randomized” corresponds to the treatment group assigned by the Interactive Response Technology (IRT) system.

- Arm A: Experimental Arm (monotherapy) nivolumab
- Arm B: Control arm Placebo

The treatment group “as treated” will be same as the treatment group “as randomized” by IRT unless a subject received the incorrect study treatment for the entire period of treatment, in which case the subject’s treatment group “as treated” will be defined as the incorrect study treatment.

Unless otherwise specified, the safety analysis will be based on the treatment group “as treated”.

Unless otherwise specified, the efficacy analysis will be based on the treatment group “as randomized”.

6.3 Populations for Analyses

- Enrolled subjects: All subjects who signed the informed consent form and obtained a subject number.
- Randomized subjects: All subjects who were randomized through the IRT.
- Treated subjects: All randomized subjects who received at least one dose of any study treatment.

Unless otherwise specified, the safety analyses will include all treated subjects.

Unless otherwise specified, the efficacy analyses will include all randomized subjects.

- Per protocol subjects: All randomized subjects who had no relevant deviation and those received at least one dose of study drug.

- [REDACTED]

[REDACTED]

[REDACTED]

[REDACTED]

[REDACTED]

[REDACTED]

[REDACTED]

[REDACTED]

[REDACTED]

7 STATISTICAL ANALYSES

7.1 General Methods

Unless otherwise noted, discrete variables will be tabulated by the frequency and proportion of subjects falling into each category, grouped by treatment. Percentages given in these tables will be rounded to the first decimal and, therefore, may not always sum to 100%. Percentages less than 0.1 will be indicated as ‘< 0.1’. Continuous variables will be summarized by treatment group using the mean, standard deviation, median, minimum, and maximum values.

Time-to-event variables (e.g. time-to resolution) will be analyzed using the Kaplan-Meier technique. When specified, the median will be reported along with 95% CI using Brookmeyer and Crowley method¹² (using log-log transformation for constructing the confidence intervals¹³).

The conventions to be used for imputing missing and partial dates for analyses requiring dates are described in [Section 8](#).

7.1.1 Adverse Events, Serious Adverse Events, Multiple events, Select Adverse Events, Other Events of Special Interest and Immune-Mediated Adverse Events

Drug-related AEs are those events with relationship to study drug “Related”, as recorded on the CRF. If the relationship to study drug is missing, the AE will be considered as drug-related.

Serious adverse events consist of AEs deemed serious by the Investigator and flagged accordingly in the CRF and clinical database.

Adverse events leading to study drug discontinuation are AEs with action taken regarding study drug(s) = “Drug was discontinued”.

Adverse events leading to dose delay are AEs with action taken regarding study drug(s) = “Drug was delayed”.

Adverse events leading to dose reduction are AEs with action taken regarding study drug(s) = “Dose was reduced”.

Adverse events will be coded using the Medical Dictionary for Regulatory Activities (MedDRA), and the most recent version of the dictionary at the time of the database lock will be used. Adverse event results will be graded for severity using the NCI Common Terminology Criteria for Adverse Events (CTCAE) and the version of the criteria specified in the protocol will be used.

In the AE summary tables, unless otherwise specified, subjects will be counted only once at the Preferred Term (PT), only once at the System Organ Class (SOC), and only once at subject level for the counting of total number of subjects with an AE. The AE tables will be sorted by the SOC and then PTs. SOC will be ordered by descending frequency overall and then alphabetically. PTs will be ordered within SOC by descending frequency overall and then alphabetically. The sorting will be done based on the ‘Any Grade’ column of the experimental arm when arms are presented side-by-side.

Unless otherwise specified, the AE summary tables will be restricted to on-treatment events regardless of the causality.

Analyses that take into account the multiple occurrences of a given adverse event will be conducted (see [Section 7.6.9](#)). To prepare these analyses, the CRF data will be processed according to standard BMS algorithms¹⁴ in order to collapse adverse event records into unique records based on the preferred term. These data will be presented as the rate per 100 person-years of exposure. These analyses will take into account all on-treatment events (allowing more than 1 event per

subject) and the total exposure time. The person-year exposure will be computed as the sum over the subjects' exposure expressed in years where the exposure time is defined as

- (Date of last dose of study treatment - date of first dose of study treatment + 31 days (or 101 days, depending on the analysis))/365.25, for subject who are off study treatment and were followed for at least 30 days (or 100 days, depending on the analysis) after last dose of study treatment.
- (Last known alive date - date of first dose of study treatment +1)/365.25, for subjects who are still on-treatment or who are off study treatment and were followed less than 30 days (or 100 days depending on the analysis) after last dose of study treatment.

7.1.1.1 Select Adverse Events (EU/ROW Submissions)

The select Adverse Events (select AEs) consist of a list of preferred terms grouped by specific category (e.g. pulmonary events, gastrointestinal events categories, etc.). AEs that may differ from or be more severe than AEs caused by non-immunotherapies and AEs whose early recognition and management may mitigate severe toxicity are included as select AEs. Categories of select AEs may include subcategories (e.g. adrenal disorders, diabetes, pituitary disorders, and thyroid disorders are subcategories of the endocrine event category).

The list of MedDRA preferred terms used to identify select adverse events is revisited quarterly and updated accordingly. The preferred terms used for the selection at the time of the database lock will be provided by categories/subcategories.

In addition to the frequency and worst severity of select AEs, time-to onset, time-to resolution, and time-to resolution where immune modulating medication was initiated will be analyzed for each specific category/subcategory of drug-related select AEs when applicable.

Further details on the definitions time-to onset and time-to resolution are described in [APPENDIX 1](#).

7.1.1.2 Other Events of Special Interest

Other events of special interest (OEOSI) consist of a list of preferred terms grouped by specific category (e.g. Myositis Event, Myocarditis Event, Demyelination Event, Guillain-Barre Syndrome, Pancreatitis Event, Uveitis Event, Encephalitis Event, Myasthenic Syndrome, Rhabdomyolysis Event, Graft Versus Host Disease). The list of MedDRA preferred terms used to identify OEOSI is revisited quarterly and updated accordingly. The preferred terms used for the selection at the time of the database lock by categories will be provided.

7.1.1.3 Immune-Mediated Adverse Events (US Submission)

In order to further characterize AEs of special clinical interest, analysis of immune-mediated AEs (IMAE) will be conducted. IMAEs are specific events (or groups of PTs describing specific events) that include pneumonitis, diarrhea/colitis, hepatitis, nephritis/renal dysfunction, rash, endocrine (adrenal insufficiency, hypothyroidism/thyroiditis, hypothyroidism, thyroiditis, hyperthyroidism, diabetes mellitus, and hypophysitis), and other specific events, considered as potential immune-mediated events by investigator that meet the definition summarized below:

- those occurring within 100 days of the last dose,
- regardless of causality,
- treated with immune-modulating medication (of note, endocrine AEs such as adrenal insufficiency, hypothyroidism/thyroiditis, hypothyroidism, thyroiditis, hyperthyroidism, diabetes mellitus, and hypophysitis are considered IMAEs regardless of immune-modulating medication use, since endocrine drug reactions are often managed without immune-modulating medication).
- with no clear alternate etiology based on investigator assessment, or with an immune-mediated component

The list of MedDRA preferred terms used to identify IMAEs is revisited quarterly and updated accordingly. The preferred terms used for the selection at the time of the database lock by categories will be provided.

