		
• Updated the abbreviations list• Revised the Appendix 2 (Safety Management Algorithms)• Added Appendix 3 (Women of Childbearing Potential and Methods of Contraception)• Other minor changes incorporated into this amendment include changes in document names, study materials that will be provided to sites, removal of duplicate statements, revisions to section numbering, and formatting changes
Administrative Letter 01	10-Feb-2016	
• Fixed the protocol title• Removed the reference to neck as an anatomical imaging area for the CT/MRI scan• Updated a section number
Original Protocol	06-Jan-2016	Not applicable

OVERALL RATIONALE FOR REVISED PROTOCOL 04

The rationale for the change to the overall survival (OS) final analysis (FA) trigger includes factors observed during the conduct of the trial. The actual OS event accrual in the study has been much slower than projected. Initial projections for the OS FA estimated [REDACTED]

Blinded

OS event tracking commenced in 2021 after the first planned interim analysis was completed. While Bristol-Myers Squibb (BMS) remains blinded to the number of OS events by treatment arm, the overall accrual of events has slowed significantly year over year, since tracking began. [REDACTED]

The treatment landscape has changed markedly since the study was designed. Patients who experience recurrence after adjuvant therapy have increased treatment options and can receive subsequent therapy with immune checkpoint inhibitors (ICI) or a combination of immune checkpoint inhibitors with chemotherapy. A portion of patients may also be cured with treatment. Increased treatment options may reduce disease mortality, therefore impacting the OS event rate.

Protocol Amendment 04 adds the option to conduct a time-driven analysis. [REDACTED]

SUMMARY OF KEY CHANGES FOR REVISED PROTOCOL 04		
Section Number & Title	Description of Change	Brief Rationale
Title Page	Updated European Union (EU) Trial Number. Updated Medical Monitor address.	Administrative update.
Synopsis Statistical Considerations	Added the option to conduct overall survival (OS) final analysis (FA) [REDACTED]	Refer to the overall rationale for revised protocol.
Section 2.1: Good Clinical Practice Section 6.1.1: Serious Adverse Event Collection and Reporting	Replaced Directive 2001/20/EC with European Regulation 536/2014.	To update the legal framework of the trial after transition to EU-CTR.

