6.2.1 Nonserious Adverse Event Collection and Reporting

The collection of nonserious AE information should begin at initiation of study drug. Nonserious AE information should also be collected from the start of a placebo lead-in period or other observational period intended to establish a baseline status for the subjects.

All nonserious adverse events (not only those deemed to be treatment-related) should be collected continuously during the treatment period and for a minimum of 100 days following discontinuation of study treatment. Nonserious AEs should be followed to resolution or stabilization, or reported as SAEs if they become serious (see [Section 6.1.1](#)). Follow-up is also required for nonserious AEs that cause interruption or discontinuation of study drug and for those present at the end of study treatment as appropriate. All identified nonserious AEs must be recorded and described on the nonserious AE page of the CRF (paper or electronic).

Completion of supplemental CRFs may be requested for AEs and/or laboratory abnormalities that are reported/identified during the course of the study.

Every adverse event must be assessed by the investigator with regard to whether it is considered immune-mediated. Immune-mediated adverse events (IMAEs) are AEs consistent with an immune-mediated mechanism or immune-mediated component for which non-inflammatory etiologies (eg, infection or tumor progression) have been ruled out. IMAEs can include events with an alternate etiology that were exacerbated by the induction of autoimmunity. Information supporting the assessment will be collected on the subject's case report form.

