5.2 Assumptions of the Treatment Effect

Assumption for DFS

An average HR of 0.72 is assumed for DFS between nivolumab and placebo in CA209577 at the final DFS analysis, which accounts for the piece-wise HRs summarized in Table 5.1-1. This translates to a median DFS of 31 months in the nivolumab arm.

In many trials studying immunotherapies, the PFS and OS curves in the immunotherapy-treated arms tend to have a delayed separation from the control arms across tumor indications;¹⁰ therefore, the treatment effect for DFS is assumed to have a delayed separation with an HR of 1 for the first 3 months and a larger treatment effect after delayed separation with an HR of 0.667. After 5 years, the treatment effect for DFS is assumed to decrease slightly with an HR of 0.8. This takes into consideration that patients who have not had disease recurrence within 5 years of surgery are generally cured from the disease and the treatment effect is more reflective of the survival benefit.

Assumption for OS

The average HR of 0.73 is assumed for OS between nivolumab and placebo in CA209577 at the final OS analysis, which accounts for the piece-wise HRs summarized in Table 5.1-2. This translates to median OS of 44 months in the nivolumab arm.

The assumption of the OS treatment effect between the 2 arms follows the same thought process as the assumption of the DFS treatment effect. The treatment effect for OS is assumed to have a delayed separation with HR of 1 for the first 4 months, and a larger treatment effect after delayed separation with an HR of 0.685. After 6 years, the treatment effect for OS is assumed to decrease slightly with an HR of 0.8. This takes into consideration the combined effect of potential for more subsequent immunotherapies in the control arm and other effective subsequent therapies in both arms for long-term survivors.

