 - On-treatment AEs will be defined as AEs with an onset date and time on or after the date and time of the first dose of study treatment (or with an onset date on or after the day of first dose of study treatment if time is not collected or is missing). For subjects who are off study treatment, AEs will be included if event occurred within a safety window of 30 days (or 100 days depending on the analysis) after the last dose of study treatment. No “subtracting rule” will be applied when an AE occurs both pre-treatment and post-treatment with the same preferred term and grade.
 - On-treatment evaluations (laboratory tests, and vital signs) will be defined as evaluations taken after the day (and time, if collected and not missing) of first dose of study treatment. For subjects who are off study treatment, evaluations should be within a safety window of 30 days (or 100 days depending on the analysis) after the last dose of study treatment.

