7.4.3.2 Subsequent Cancer Therapy

Number and percentage of subjects receiving subsequent therapies will be summarized. Categories include:

- Immunotherapy including commercial Nivolumab (anti-PD1 agents, anti-PD-L1 agents, anti-CTLA-4 agents and others) by drug name
- Other anti-cancer agents excluding all immunotherapy (approved and investigational) by drug name
- Surgery for treatment of tumors
- Radiotherapy for treatment of tumors
- Any combination of the above

A subject listing of follow-up therapy will also be produced for subjects who had any subsequent therapy.

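### The 100-day IMAE tables and the all-cause OEOSI table have no visible cut or flag at subsequent therapy, so they can count toxicity from a checkpoint inhibitor started after recurrence

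*SAP*

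**What the plan says.** SAP 6.1 sets the post-treatment window from the last dose of study treatment alone: "AEs will be included if event occurred within a safety window of 30 days (or 100 days depending on the analysis". SAP 7.1.1 makes adverse event tables all-cause unless stated otherwise.

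SAP 7.1.1.3 defines IMAEs as "those occurring within 100 days of the last dose", counted "regardless of causality". They must be treated with immune-modulating medication (endocrine events are exempt) and must be "with no clear alternate etiology based on investigator assessment, or with an immune-mediated component". SAP 7.6.7 tabulates them over 100 days. SAP 7.6.8 plans two 100-day OEOSI tables, one all-cause and one drug-related.

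Subsequent therapy is summarized separately in SAP 7.4.3.2, with a category for "Immunotherapy including commercial Nivolumab (anti-PD1 agents, anti-PD-L1 agents, anti-CTLA-4 agents and others) by drug name". No visible text links those dates to the adverse event tables.

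On conduct, Protocol 3.5 stops study drug at recurrence. Protocol 3.4.1 bars other anticancer treatment only until recurrence. Protocol 6.2.1 collects adverse events for at least 100 days after discontinuation, with no stop at new therapy.

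**The concern.** A subject who recurs stops study drug and may start a new systemic treatment while the 100-day window is still open. If that treatment is a checkpoint inhibitor, its toxicity is of the kind the IMAE tables are meant to capture. A placebo subject who recurs, starts commercial nivolumab and then has steroid-treated pneumonitis inside 100 days could appear as a placebo IMAE. A thyroid event could qualify even without immune-modulating medication.

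Two things are at stake. Both absolute rates may include events caused by a drug outside the study. The contamination also depends on recurrence, which the treatment is meant to reduce, so the nivolumab-minus-placebo difference may be pulled toward zero. The same events feed the IMAE onset and resolution summaries (7.6.7) and the immune-modulating medication summaries (7.4.3.1).

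The efficacy plan treats the parallel problem explicitly. Primary DFS is censored at new anticancer therapy (SAP 4.1.1), and a sensitivity analysis lifts that rule (7.5.2.1). The visible safety plan has only the uncut version.

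**Working it through.** **Can such an event pass the IMAE definition?**

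- Timing: if recurrence is found 14 to 28 days after the last dose (one dosing interval), 100 - 14 = 86 to 100 - 28 = 72 days of the window remain.
- Causality: not a condition.
- Etiology: the condition is "with no clear alternate etiology based on investigator assessment, or with an immune-mediated component". An investigator could name the commercial drug as the other cause. The second limb can still admit the event, because checkpoint-inhibitor toxicity is immune-mediated. Protocol 6.2.1 asks only for events "for which non-inflammatory etiologies (eg, infection or tumor progression) have been ruled out", and a second checkpoint inhibitor is not a non-inflammatory cause. Investigators are also blinded (Protocol 4.6), which makes it harder to call the later drug the clear cause.

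So the event can be counted, but need not be.

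**How large could the effect be?** The plan states no figure for this, so the following is an illustration.

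Inputs from the documents: 760 subjects randomized 2:1, about 507 to nivolumab and 253 to placebo, with the DFS hazards of SAP Table 5.1-1. First the table's 12-month DFS rates are reproduced:

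- Placebo: exp(-0.035 × 12) = exp(-0.42) = 65.7%, as stated.
- Nivolumab: exp(-(0.035 × 3 + 0.035 × 0.667 × 9)) = exp(-0.315) = 73.0%, as stated. The rounded hazard of 0.023 gives 73.2%.

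DFS events by 12 months are therefore 34.3% on placebo (0.343 × 253 = 87) and 27.0% on nivolumab (0.270 × 507 = 137).

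Assumptions, none of them in the documents:

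- a = 30-70% of these subjects start systemic therapy inside the window;
- b = 10-40% of those receive a checkpoint inhibitor;
- g = 20% of those have a qualifying IMAE.

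The rise in incidence is (event proportion) × a × b × g. The product a × b runs from 0.3 × 0.1 = 0.03 to 0.7 × 0.4 = 0.28.

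| | Low | High |
|---|---|---|
| Placebo subjects exposed | 87 × 0.03 = 2.6 | 87 × 0.28 = 24.4 |
| Placebo, rise in points | 34.3 × 0.03 × 0.20 = 0.2 | 34.3 × 0.28 × 0.20 = 1.9 |
| Nivolumab, rise in points | 27.0 × 0.03 × 0.20 = 0.16 | 27.0 × 0.28 × 0.20 = 1.5 |
| Shrinkage of the difference | (34.3 - 27.0) × 0.006 = 0.04 | (34.3 - 27.0) × 0.056 = 0.4 |

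The last row assumes equal a, b and g in both groups. If no nivolumab subject received a later checkpoint inhibitor, the shrinkage would equal the whole placebo rise, 0.2-1.9 points. That is the ceiling under these fractions.

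The inputs are imperfect. DFS events include deaths, which overstates the number who switch. Subjects who finish the year and recur in the next 100 days are left out. The 20% risk is not scaled to the roughly 10-12 weeks that remain.

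**The case against.** A reader might infer that every such event is charged to the study arm. The etiology condition in SAP 7.1.1.3 does not support that: commercial nivolumab started weeks before onset is an obvious alternative cause, and an investigator may exclude the event. This stands, and the claim is limited to what can be counted.

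A reader might also infer that the documents expect heavy checkpoint-inhibitor use inside the window, mostly in controls. They do not show this. The remark in SAP 5.2 on "potential for more subsequent immunotherapies in the control arm" explains the weaker OS effect assumed after 6 years. The statement in the rationale for Revised Protocol 04 that patients "can receive subsequent therapy with immune checkpoint inhibitors (ICI" belongs to an April 2024 amendment. The first interim analysis was projected about 12 months after the last randomization (SAP 5.4) and was complete by 2021. With one year of dosing at most, nearly all the 100-day windows would have closed long before that amendment. SAP 7.4.3.2 lists reporting categories and gives no timing.

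Much of the safety plan is less exposed. The second OEOSI table and the only 100-day table in 7.6.5 are restricted to drug-related events. Select adverse events, serious events and discontinuations use 30 days (7.6.2, 7.6.3, 7.6.6.1). The planned listings of IMAEs, OEOSI and follow-up therapy would let a reader find overlaps by hand. Safety is an exploratory objective analyzed descriptively, so the documents do not support calling the IMAE contrast the main safety result.

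Two further points stand. Safety groups are as treated (SAP 6.2), which differs from as randomized only if a subject had the wrong drug throughout. Parts of the SAP are redacted, so a rule there cannot be ruled out.

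What remains is that no visible summary separates these events, and the etiology condition does not do so reliably.

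**Conclusion.** The point holds in a limited form. The 100-day IMAE tables and the all-cause OEOSI table can include toxicity from therapy started after recurrence, in either treatment group. Under the assumed fractions each group's IMAE rate is inflated by at most about 2 points, and the difference by a few tenths of a point when use is equal. A larger distortion needs unequal checkpoint-inhibitor use inside the window, which the documents neither quantify nor establish. They therefore do not support a conclusion that the planned tables would materially hide the immune toxicity of adjuvant nivolumab. No figure is offered for OEOSI. This is a low-priority improvement that would show whether the contamination is negligible.

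**What to change.** Keep the planned tables. In SAP 7.6.7, and for the all-cause table of 7.6.8, add a supportive version that excludes events with onset on or after the first dose of subsequent systemic anticancer therapy. Report the number of events and subjects excluded by arm, and flag these events in the IMAE and OEOSI listings. Section 7.6.5 needs no change.

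The cost is a short SAP addition and a repeat run of existing tables. No new data are needed. Protocol Table 5.1-3 reviews adverse events and subsequent therapy at FU1 (day 30) and FU2 (84 days later), nominally day 30 + 84 = 114. Even with both visits 7 days early, FU2 falls at day 23 + 77 = 100, so the whole window is covered.

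The downside is that the added version also drops some genuine delayed study-drug toxicity in subjects who switch therapy, and these are mainly subjects who recur. It should therefore be labelled supportive and should not replace the planned tables.
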